8.5 Halting Criteria: Safety Concerns

The trial will be halted (paused) for a safety review by the DMC if there are 2 or more Serious Adverse Reactions.

9 CLINICAL MONITORING

Site monitoring will be conducted to ensure that human subject protection, study procedures, laboratory procedures, study intervention administration, and data collection processes are of high quality and meet sponsor, GCP/ICH, and regulatory guidelines, and that the study is conducted in accordance with the protocol and DCRI sponsor standard operating procedures. The IND sponsor, or as detailed in the Transfer of Regulatory Obligations (TORO), NIH, FDA, or its designee will conduct site-monitoring visits as detailed in the monitoring plan or in the manual of procedures.

Site visits will be made at standard intervals as defined by the site monitoring plans and may be made more frequently as directed by the IND sponsor. Monitoring visits will include, but are not limited to, review of regulatory files, accountability records, CRFs, informed consent forms, medical and laboratory reports, and protocol compliance. Study monitors will meet with investigators to discuss any problems and actions to be taken and document visit findings and discussions.

10 STATISTICAL CONSIDERATIONS

10.1 Study Endpoints

Efficacy Categories for IH volume:

Progressive disease: >20% *increase* in hemangioma volumetric size

Partial response: >20% and up to 80% *reduction* in volumetric size of hemangioma

Complete/near complete response: >80-100% *reduction* in volumetric size of hemangioma

Stable disease: none of the above or between 20% *increase* in hemangioma volumetric size and 20% *reduction* in volumetric size

Efficacy Categories for IH Color:

Progressive disease: >30% *increase* in hemangioma color

Partial response: >30% and up to 80% *reduction* in color of hemangioma

Complete/near complete response: >80-100% *reduction* in color of hemangioma

Stable disease: none of the above or between 30% *increase* in hemangioma color and 30% *reduction* in color

Complete/ Near Complete Response	Partial Response	Stable Disease	Progressive Disease
+100		0	-100

Visual Analog Scale (VAS)²¹: 100 mm scale used to independently grade volume and color

-100 indicates hemangioma has doubled in volumetric size/color: twice as intense

0 indicates no change

+100 indicates complete shrinkage or complete resolution of volumetric size/color

The **partial response** or greater of hemangioma will be based on centralized VAS-volume and VAS-color scores from baseline to Day 180 in both treatment arms assessed by three independent, expert and masked pediatric dermatologists (Section 6.6).

Example of partial response in VAS- volume after 32 days of timolol treatment.

Primary Efficacy Endpoints:

Estimation of the proportion of infants with partial response in hemangioma volume (partial response or greater as assessed by VAS-volume) from baseline to day 180 within each randomized treatment arm and compared with the untreated controls.

Secondary Endpoints:

Secondary **efficacy** endpoints will include the following:

1. Estimation of the proportion of infants with partial response in hemangioma color (partial response or greater as assessed by VAS-color) from baseline to day 180 within each randomized treatment arm and compared with the untreated controls.
2. Comparison of partial response of hemangioma volume (partial response or greater as assessed by VAS-volume) between the two treatment arms.
3. Comparison of partial response of hemangioma color (partial response or greater as assessed by VAS-color) between the two treatment arms.
4. Absolute change in hemangioma dynamic complication scale from Day 0 to end of study within each treatment arm.
5. Assess time to partial response by comparing baseline to day 30, day 60, day 120 and day 180 in both treatment arms.
6. Absolute change in IH-QoL score scale from Day 0 to end of study within each treatment arm.

Secondary **safety** endpoints are the rate of serious adverse events and adverse events of special interest (Section 8.1.2) from randomization to Day 180 in infants treated with topical timolol maleate (0.25% and 0.5%) GFS for the treatment of infantile hemangioma.

Exploratory Endpoints:

Exploratory PK endpoints include estimation of PK parameters such as clearance (CL), volume of distribution (V), area under the curve (AUC), and maximum concentration (C_{max}), as possible.

The relationship between different hemangioma characteristics and plasma concentrations may also be described as an exploratory endpoint.

Treatment Failure for Partial Response in Hemangioma Color or Volume

The infant will be considered a treatment failure for the primary endpoint of partial response of VAS-volume or the secondary endpoint of partial response of VAS-color from baseline to Day 180 if any of the following conditions are met:

1. Partial response not achieved at the Day 180 visit in infants who complete the 180-day treatment period.
2. Infant withdrawn from masked treatment due to progressive disease. This will include participants randomized to the 0.25% treatment arm and switched to the 0.5% treatment arm.
3. Ulceration of the target hemangioma after initiation of masked treatment.
4. Infant withdrawn from study treatment due to safety concerns.
5. Study drop-out or loss to follow-up after the 30-day visit and before the 180-day visit for reasons other than progressive disease, ulceration, or safety concerns without having achieved partial response at the last study visit before drop-out.

Partial response will not be evaluated in participants who drop-out from the study for reasons other than progressive disease, ulceration, or safety concerns or are lost to follow-up before the 30-day visit. Sensitivity analyses will be performed to assess the impact of assumptions made to account for drop-out on the primary analysis. This will include summaries of partial response that exclude participants who withdrew for reasons other than lack of efficacy. Other methods, such as multiple imputation, may be considered based on drop-out rates and cause of missingness.

In addition to the assessments of partial response through the 180-day visit, the proportion of participants who achieve partial response through each study visit will be summarized. The number of participants with partial response before but not at the 180-day visit will be summarized.

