5.3.3 Reasons for Participant Withdrawal

5.3.4 Withdrawal from Treatment Phase (study drug dosing)

The clinician or family may choose to suspend study drug dosing for any reason during the study period, and the infant will remain in the study.

If at any time during the study, the treating physician determines that the target hemangioma failed therapy and the IH requires more aggressive surgical or alternate pharmacologic therapy (e.g., oral beta blockers, or oral or topical corticosteroids), the infant may be withdrawn from the Treatment Phase and move into the 7 day safety follow-up period. If the participant continues to participate in the study, they will be followed for safety for 7 days after last study dose, and should continue to return for planned study visit activities including photography of the IH.

If a treating physician chooses to withdraw the participant from the Treatment Phase (i.e. discontinue timolol maleate GFS dosing), the treating physician must immediately report this to the DCRI study PI and Protocol Chairs.

The investigator will withdraw a participant from receiving further study drug if:

1. Any clinically significant adverse event (AE) is deemed by the principal investigator to require discontinuation of study drug.
2. The treating physician determines that the target hemangioma failed therapy and requires alternate pharmacologic, laser or surgical intervention.
3. Participant develops ulceration of the target hemangioma after therapy is initiated.
4. Participant receives oral or intravenous corticosteroids or additional oral, intraocular, or topical beta blockers for treatment of any other conditions.
5. Requested by the NIH, FDA, DMC, or PTN.

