5.3.6 Disease Progression Unmasking

Infants enrolled in the treated arms who are determined by the treating physician to have progressive disease will be unmasked and:

- If on 0.25% timolol maleate GFS they will receive open label 0.5% timolol GFS two times a day.
- If on 0.5% timolol maleate GFS the investigator may choose to continue study treatment with 0.5% open label, or withdraw the infant from the Treatment Phase and proceed directly into the 7 day safety follow-up period. Participants may receive alternate therapies during the safety follow-up period.

Infants that are unmasked and receive open label 0.5% timolol maleate GFS will continue to be photographed and followed per the schedule of study procedures (Table 6-1).

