6.5 Follow-up Period

For treated participants, a follow-up period through day 7 (+5 days) after completing study drug or last study procedure, as applicable, will include solicitation of concomitant medications and assessment of adverse events/AEs of special interest.

For all treated participants that complete 180 days of treatment on study drug, the follow-up period through day 90 (± 5 days) after study drug has been completed, will include solicitation of timolol dosing information and adverse events of special interest.

If a participant's last day of treatment phase ends after day 180 (+5 days) (e.g., out-of-window visit), site staff should continue the follow-up period for the full 90 days post last dose.

Infants who participate in the non-intervention cohort, will have no further follow up beyond 180 days.

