8.1.4 Identification of Events and Timeframe for Reporting

Pre-existing conditions will not be considered as adverse events. New events that occur or pre-existing conditions that worsen in terms of frequency or intensity will be reported as adverse events.

All reportable events as defined above, determined to be an AE based on physical examination, laboratory findings, or other means, will be reported in the electronic case report form (e-CRF). The investigator will provide the date of onset and resolution, intensity, action(s) taken, changes in study drug dosing, relationship to study drug, and outcome.

Any event excluding adverse events of special interest beginning more than 7 days after the last dose of study drug or last study procedure will not be reported. For participants in the treatment arm adverse events of special interest only will be reviewed and reported at 90 days after the last dose of study drug.

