10.4 Analysis Plan

10.4.1 Population for Analysis

All randomized infants who received study dose and non-randomized participants enrolled in the untreated control cohort will be included in the intent-to-treat population. The primary analysis will use the intent-to-treat population with treatment group determined by randomization assignment.

All infants enrolled and receiving at least one dose of timolol therapy will be included in the safety population and the safety analysis. All infants who had at least one interpretable PK sample will be included in the PK analysis.

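### The topical timolol safety rate does not separate events that begin after a switch to another therapy, so it can include some effects of oral beta blockers

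*Combined protocol and SAP*

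**What the plan says.** **Endpoint, population and analysis.** The secondary safety endpoint in Section 10.1 is "the rate of serious adverse events and adverse events of special interest (Section 8.1.2) from randomization to Day 180", counted in infants treated with either strength of topical timolol. Section 10.4.1 states: "All infants enrolled and receiving at least one dose of timolol therapy will be included in the safety population and the safety analysis". Section 10.4.6 summarizes the proportion of infants with AESIs and tests event rates between arms as an exploratory analysis. None of the three mentions a change of therapy.

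**Routes to another therapy.** Section 5.3.4 foresees withdrawal from the Treatment Phase when the lesion "requires more aggressive surgical or alternate pharmacologic therapy (e.g., oral beta blockers, or oral or topical corticosteroids". Section 5.3.6, on infants in the 0.5% arm who leave after progression, adds: "Participants may receive alternate therapies during the safety follow-up period". Section 4.1 agrees. Section 7.4, however, lists oral and intravenous beta blockers as not permitted during the study.

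**Collection after the last dose.** Sections 6.5 and 8.1 collect all adverse events through 7 (+5) days after study drug or the last study procedure, as applicable. Section 8.1.4 exempts AESIs from its 7-day limit and says that, for the treatment arm, "adverse events of special interest only will be reviewed and reported at 90 days after the last dose of study drug". The synopsis and Section 4.2 also describe 90 days of AESI monitoring after the last dose. Sections 6.5 and 8.1 restrict the 90-day contact to infants who complete 180 days of treatment. Section 5.3.4 follows withdrawn infants for safety for 7 days but asks them to keep attending planned visits, and Table 6-1 schedules adverse event assessment at those visits.

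**The concern.** The secondary objective is to describe the safety of topical timolol. An infant who stops it and starts an oral beta blocker a few days later has a new systemic exposure to the same drug class while still inside the counting window. Section 2.3.1.2 lists bronchial hyperreactivity, hypotension, bradycardia, hypoglycemia and sleep disturbance as effects of systemic beta blockade. These correspond to five of the ten AESIs in Section 8.1.2. An event caused by the oral drug would enter the numerator of the topical rate, and only in infants for whom topical treatment had failed.

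The plan already handles switching for efficacy: 10.1 classes it as treatment failure, and 10.4.4 analyzes scores after the move to open-label treatment separately. Safety has no counterpart.

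The arms also leave masked treatment by different routes. On progression, infants on 0.25% go to open-label 0.5%, while those on 0.5% may go straight to alternate therapy. Section 5.3.4 allows withdrawal for failure in either arm, but even with equal progression rates the post-switch events could fall unevenly and affect the exploratory between-arm test.

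**Working it through.** **1. The planned precision reproduces.** Section 10.3 assumes 20% of infants with an AESI and 5% with a serious event of special interest, n = 100. The Wilson 95% interval is [p + z²/2n ± z√(p(1−p)/n + z²/4n²)] / (1 + z²/n), with z = 1.96.

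- p = 0.20: 0.133 to 0.289, width 0.156 (plan: 0.13 to 0.29, width 0.16).
- p = 0.05: 0.022 to 0.112, width 0.090 (plan: 0.02 to 0.11, width 0.09).

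**2. Does a post-switch event count?** Take an infant withdrawn for failure on Day 60 who starts an oral beta blocker on Day 62 and has bradycardia on Day 65. Onset is 65 − 60 = 5 days after the last dose, so it is collected on every reading of the protocol. It precedes Day 180 and the infant received at least one dose, so it is counted. Causality does not enter the definition of the rate.

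**3. How long can such events accrue?**

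- *Narrow reading* (5.3.4, 6.5, 8.1): an infant withdrawn early is followed for 7 (+5) days after the last dose and gets no 90-day contact.
- *Broad reading* (synopsis, 4.2, 8.1.4): AESIs are followed for 90 days. For the infant above that reaches Day 60 + 90 = Day 150, still inside the endpoint.
- The alternative of the last study procedure as the starting point, together with continuing visits, leaves it unclear when even the 7-day clock starts.
- Serious events that are not AESIs fall outside reporting once they begin more than 7 days after the last dose, if the clock runs from that dose.

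**4. Illustrative size.** The documents give neither the share moving to an oral beta blocker nor their event rate, so both are assumptions. Let r be the AESI rate on topical timolol (20%, from 10.3), s the share who switch, and q the chance of a first counted AESI after the switch among infants event-free until then. Switching is taken as unrelated to having already had an AESI.

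Observed rate = r + s(1 − r)q

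| s | q | Observed AESI rate | Wilson 95% interval, n = 100 |
|---|---|---|---|
| 5% | 10% | 0.20 + 0.05×0.8×0.10 = 20.4% | 0.137 to 0.293 |
| 10% | 30% | 0.20 + 0.10×0.8×0.30 = 22.4% | 0.153 to 0.315 |
| 20% | 40% | 0.20 + 0.20×0.8×0.40 = 26.4% | 0.19 to 0.36 |

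The shift is 0.4 to 6.4 points, against a planned half-width of 0.156/2 = 7.8 points. A q of 30% or 40% is hard to reach in about a week and in practice needs the broad reading in step 3.

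**The case against.** **Few infants may switch.** Eligibility requires thin lesions of at most 10 cm² and excludes hemangiomas needing systemic therapy. Progressors on 0.25% go to open-label topical 0.5%, and those on 0.5% may stay on it. In the largest prospective study described in Section 2.1, growth was controlled or the lesion regressed in 36 + 56 = 92 of 101 treated infants, leaving 9 (about 9%), not all of whom would need oral therapy. This stands and points to the lower part of the range.

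**Counting all events in exposed infants is conventional.** It is a cautious choice for a descriptive objective, and the between-arm test is only exploratory. This also stands, and is why the all-events rate should remain. It does not make the topical rate separable.

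**The data to separate events are already collected.** Onset date and relationship to study drug are recorded, and concomitant medications are taken through the call after Day 180. True, but no planned summary uses them for this purpose.

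Some stronger readings are tempting but not supported:

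- *Every adverse event after a switch counts to Day 180.* Sections 5.3.4, 6.5, 8.1 and 8.1.4 limit collection, and they disagree on how far.
- *The Day 270 call biases the rate.* Section 6.5 says this contact "will include solicitation of timolol dosing information and adverse events of special interest", and the concomitant medication row of Table 6-1 stops one visit earlier. But the contact is for infants who complete 180 days, whose later events lie outside an endpoint that ends at Day 180.
- *The rate could reach 28%.* Adding 20 × 40% = 8 infants to 20 ignores switchers who have already had an AESI. The formula above gives 26.4%.
- *Topical timolol must look worse than it is.* Ending collection soon after withdrawal also removes events, so the net direction is not established.
- *The AESI list as a whole is a beta-blockade list.* Five of ten match. Section 2.3.1.2 links irritation to topical use, and the other four are not on its systemic list.

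**Conclusion.** The point holds for AESIs, and for serious events within the week or so after the last dose. As written, the secondary safety rate can include oral beta-blocker effects, and nothing in 10.1, 10.4.1 or 10.4.6 separates them. Any effect on the between-arm comparison is possible through the unequal exits, but its direction and size are unknown.

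The size cannot be calculated from the documents and is probably small: 20.4% to 26.4% in place of 20%, if 5% to 20% switch and 10% to 40% of those still event-free then have a first AESI. The upper end depends on AESI collection well beyond 7 days after withdrawal, which the protocol does not settle. This is an inexpensive improvement in interpretability, worthwhile because Section 2.1 says the results may be used for labeling. It does not invalidate the safety analysis.

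**What to change.** In Sections 10.1 and 10.4.6:

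1. Report SAEs and AESIs with onset from first dose to the earlier of (a) last study dose plus 7 days or (b) first dose of another systemic beta blocker or another hemangioma therapy. State that open-label topical 0.5% counts as study drug for this rule.
2. Report later events in a separate table, by therapy received.
3. Keep the present randomization-to-Day-180 rate beside them, and show the on-treatment version by arm next to the exploratory test.

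The adverse event onset dates and the concomitant medication records already collected are enough. The cost is SAP wording and one further table. The downside is that a delayed topical effect appearing soon after a switch moves to the second table, which is why the all-events rate stays.

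Two sets of sections should also be reconciled, without this review taking a position on the clinical rule: the synopsis, 4.2, 5.3.4, 6.5, 8.1 and 8.1.4 on which events are collected after withdrawal, for how long and from which starting point; and 7.4 with 5.3.4 and 5.3.6 on beta blockers while an infant remains in the study.

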3.1.2 Secondary Outcome Measures

1. Efficacy

- Partial response of hemangioma color from baseline to 180 days within each treatment arm and compared with untreated controls
- Comparison of partial response of hemangioma volume from baseline to 180 days between the two treatment arms
- Comparison of partial response of hemangioma color from baseline to 180 days between the two treatment arms
- Improvement of hemangioma complication in infants within each treatment arm
- Assess time to partial response by comparing baseline to day 30, day 60, day 120 and day 180 in both treatment arms
- Hemangioma Quality of Life assessment for infants within each treatment arm

- ###### 2. Serious adverse events and adverse events of special interest in infants treated with topical timolol maleate (0.25% and 0.5%) GFS for the treatment of infantile hemangioma

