8 ASSESSMENT OF SAFETY

8.1 Methods and Timing for Assessing, Recording and Analyzing Safety Parameters

Safety will be assessed in all infants following initial study-specific procedure through 7 days (+5 days) post last study dose or last study procedure, as applicable, and will be assessed by frequency and incidence of AEs and SAEs. Those outpatient infants whose parents are willing and able to remain in clinic for a period of 2 hours after the initial application of timolol will also have vital signs (heart rate and blood pressure) collected at 1 hour and 2 hours (+/- 15 mins). The infant will be monitored for signs and symptoms of an AE or AE of special interest during this period, particularly bronchospasm, arrhythmias, and hypoglycemia.

Inpatient infants will be monitored by hospital staff. Hospital staff will collect vital signs (heart rate and blood pressure) 1 and 2 hours after the initial application of timolol and monitor for signs of an AE or AE of special interest during this period.

For all treated participants that complete 180 days of treatment on study drug, the follow-up period through day 90 (± 5 days) after study-specific drug has been completed will include solicitation of adverse events of special interest only. Infants whose parents decline treatment with timolol will have no further follow up beyond 180 days. Refer to Figure 1 and Table 6-1. A safety monitoring committee (DMC) will be convened by NIH to review data and safety information from study infants throughout the study.

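### The Day-180 safety endpoint, the last-dose clock for collecting events and the all-dosed denominator do not match, so early stoppers may count in the rate without being observed to Day 180

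*Combined protocol and SAP*

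**What the plan says.** **Endpoint.** Section 10.1 sets the secondary safety endpoint as the rate of SAEs and AESIs "from randomization to Day 180 in infants treated with topical timolol maleate". Section 3.1.2 lists the same outcome with no time window. Neither section says whether a rate is a proportion of infants or a count per unit of time.

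**Collection of all events.** Section 8.1 assesses safety from the first study-specific procedure "through 7 days (+5 days) post last study dose or last study procedure". Section 8.1.4 gives the matching exclusion: "Any event excluding adverse events of special interest beginning more than 7 days after the last dose of study drug or last study procedure" is not reported.

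**Collection of AESIs.** Section 8.1.4 says of treatment-arm participants that "adverse events of special interest only will be reviewed and reported at 90 days after the last dose of study drug", with no condition on completing treatment. The synopsis and Section 4.2 likewise describe 90 days of AESI monitoring for the treatment arms. Sections 6.5 and 8.1 are narrower: "For all treated participants that complete 180 days of treatment on study drug, the follow-up period through day 90" is how both introduce the 90-day period.

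**Early stoppers.** Section 5.3.4 says that infants withdrawn from the Treatment Phase who remain in the study will be treated as follows: "they will be followed for safety for 7 days after last study dose, and should continue to return for planned study visit activities". Under Section 5.3.6, infants switched to open-label 0.5% stay on the full schedule.

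**Analysis.** Section 10.4.1 puts every infant with at least one dose in the safety population. Section 10.4.6 plans numbers and percentages of AEs and SAEs, the proportion of infants with AESIs, and an exploratory test of equal event rates between arms. It gives no time window, no person-time or time-to-event summary, and no rule for infants whose collection ends before Day 180.

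**The concern.** The endpoint runs on a calendar clock, collection runs on a last-dose clock, and the denominator ignores both. Two things follow.

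- **Early stoppers.** An infant who stops dosing at Day 60 may have reporting of events other than AESIs end at about Day 67. AESI collection ends at about Day 67 under Sections 6.5 and 8.1, or at Day 150 under Section 8.1.4. Neither reaches Day 180, but the infant counts as a full member of a Day-180 proportion.
- **Completers.** Section 6.5 expects some treatment phases to run past Day 180 (+5). Events on drug after Day 180, events in the 7 days after the last dose, and AESIs up to 90 days after it are collected, but no endpoint covers them.

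Observation time could also differ by arm. On progression, Section 5.3.6 keeps infants from the 0.25% arm on the visit schedule, while infants on 0.5% may be withdrawn into the 7-day follow-up. Section 10.4.6 then compares crude event rates between the arms. Safety is the only secondary objective, and Section 2.1 says the results may be used in labeling negotiations, so the rate should have a stated window that the data fill.

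**Working it through.** **1. The plan's own safety figures.** Section 10.3 assumes 100 treated infants, a 20% AESI rate and a 5% rate of SAEs of special interest. The 95% Wilson interval for 20/100 is (0.133, 0.289), width 0.155. For 5/100 it is (0.022, 0.112), width 0.090. The chance of at least one event is 1 − 0.99^100 = 0.634 at a 1% risk and 1 − 0.95^100 = 0.994 at a 5% risk. All agree with the stated figures after rounding.

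**2. Model for early stopping.** The documents give no stopping times and no hazard, so the following are assumptions:
- The hazard is constant, reaches the planned risk P at Day 180, and continues unchanged after the drug stops: λ = −ln(1 − P)/180.
- A share d of infants stops at day s and is observed to day s + k. Here k = 7 for AESIs under Sections 6.5 and 8.1, and k = 90 under Section 8.1.4.
- Crude proportion = (1 − d)·P + d·[1 − exp(−λ(s + k))].

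The values d = 10% and 20% are scenarios. Section 10.3 allows up to 10% drop-out, but for unevaluable response. Section 5.3.1 uses 20 withdrawals as a trigger for adding infants.

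**3. AESIs, P = 0.20.** λ = 0.22314/180 = 0.0012397 per day. The risk accrued is 0.0448 by Day 37, 0.0797 by Day 67, 0.1382 by Day 120 and 0.1697 by Day 150.

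| Scenario | AESIs collected to +7 days | AESIs collected to +90 days |
|---|---|---|
| 10% stop at Day 60 | 0.9×0.20 + 0.1×0.0797 = 18.8% | 0.9×0.20 + 0.1×0.1697 = 19.7% |
| 20% stop at Day 60 | 0.8×0.20 + 0.2×0.0797 = 17.6% | 0.8×0.20 + 0.2×0.1697 = 19.4% |
| 20% stop at Day 30 | 0.8×0.20 + 0.2×0.0448 = 16.9% | 0.8×0.20 + 0.2×0.1382 = 18.8% |

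The shortfall is 0.3 to 3.1 points. In the limit where no stopper's event is seen, the crude figure is 0.9×0.20 = 18% or 0.8×0.20 = 16%.

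**4. SAEs, using 5% as the planning rate and the 7-day limit.** λ = 0.05129/180 = 0.00028496. The risk accrued is 0.0105 by Day 37 and 0.0189 by Day 67. The same three scenarios give 4.7%, 4.4% and 4.2%.

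**5. Sensitivity to the constant hazard.** If 80% of the AESI risk falls before observation ends at Day 37, the crude figure is 0.9×0.20 + 0.1×0.16 = 19.6%, or 0.8×0.20 + 0.2×0.16 = 19.2%. If no excess risk remains once the drug is stopped, the crude figure already counts the events that treatment caused.

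**6. Would a last-dose window alone cure it?** No. The risk to Day 187 with full follow-up is 1 − exp(−0.0012397×187) = 20.7%. With stopping at Day 60 and collection to +7 days, the proportion is 0.9×0.2069 + 0.1×0.0797 = 19.4%, or 0.8×0.2069 + 0.2×0.0797 = 18.1%. A rate per unit of time does cure it under the same model. For an infant observed to day t, the expected number of first events is 1 − exp(−λt) and the expected time at risk is [1 − exp(−λt)]/λ. The ratio is λ for any mix of t, or 0.0012397×30 = 0.037 first events per infant-month.

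**The case against.** A reader might infer that the plan simply understates the safety rate. The documents do not support that, for four reasons.

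- **Later events do not bias a Day-180 rate.** Events after Day 180 belong to a different, longer-window quantity. Nor are they discarded: Section 10.4.6 sets no Day-180 cut-off and may well report them. Table 6-1 also records standard-of-care timolol use at the follow-up contacts, so keeping that period apart is defensible. This stands. What is missing is a defined endpoint for those events.
- **Early stoppers are not always lost.** Switched infants stay on schedule. Withdrawn infants who remain in the study should keep attending visits, Table 6-1 lists adverse events at each visit, and the alternative limit of the last study procedure in Sections 8.1 and 8.1.4 may extend collection. This stands in part. Section 5.3.4 also limits their safety follow-up to 7 days after the last dose, so the text is ambiguous.
- **Direction depends on risk after stopping.** If risk falls when the drug stops, or if the target is on-treatment risk, the shortfall is small or nil. An infant withdrawn for an adverse event already has that event counted. This stands.
- **The 7-day cut may not apply to AESIs.** The larger shortfalls in the first column of the table need the narrower reading in Sections 6.5 and 8.1. Under Section 8.1.4 they shrink to the second column. This stands, and it shows why those sections need to agree.

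The safety objective is also descriptive, and the between-arm test is exploratory, which limits the consequence.

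**Conclusion.** The mismatch is in the text: a Day-180 endpoint, collection counted from the last dose, every dosed infant in the denominator, and only counts and proportions planned. The sections also disagree on whether early stoppers have 90 days of AESI follow-up.

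The numerical effect is conditional and small. In the scenarios shown, the crude AESI figure falls short of 20% by 0.3 to 3.1 points, against a planned interval 15.5 points wide. That range rests on assumed stopping shares and times and on an unchanged constant hazard after stopping; none of these comes from the documents. An unconditional statement that the rate is understated would go too far. This is a minor point, worth correcting because the correction is cheap and makes the between-arm comparison easier to interpret.

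**What to change.** In Sections 10.1 and 10.4.6:

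1. Define the on-treatment safety window as first dose to last dose + 7 days, and state what is meant by a rate.
2. Report, by arm, the proportion of infants with SAEs and with AESIs together with events per infant-month of observation. The proportion alone does not correct for unequal follow-up.
3. Report AESIs from 7 to 90 days after the last dose as a separate post-treatment rate, noting any standard-of-care timolol use.

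Reconcile Sections 6.5 and 8.1 with Section 8.1.4 on AESI follow-up for infants who stop early.

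The cost is SAP wording and one or two extra tables built from data that the plan already collects. The drawback is that a rate per infant-month assumes a roughly constant hazard. If events cluster soon after the first doses, it should be read beside the proportion and not in place of it.
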